Patients for whom informed consent has been obtained will be randomized to IL or SMOF using REDCap software. Treatment allocation per randomization (IL versus SMOF) will remain in effect through the intervention period: until the 2nd blood sample at 3 g/kg/day or 2 weeks of age, whichever comes first. Clinicians cannot be masked to the lipid emulsion – see safety precautions, below

Blood samples for the study will be obtained with blood draws for clinical measurement of bilirubin and/or triglyceride levels such that the study will not require additional interventions for blood sampling – see blood sampling schema below. When treated with 3 g/kg/day, blood will not be sampled if patients have received a mixture of SMOF and IL in the preceding 24 hours, or if SMOF or IL infusions were interrupted for ≥ 2 hours in the preceding 24 hours. Daily weights and serum bilirubin and triglyceride levels will be abstracted from the medical record.

This study will also include measurements that were not included in previous studies in order to validate measures and obtain a fuller picture cause and effect mechanisms. These measures include serum albumin, bilirubin binding capacity, reserve bilirubin binding capacity, and 2 methods for measuring free fatty acid – both bound and unbound free fatty acids. Serum for FFAu and Bf and albumin, will be stored at -80 C and shipped to Fluoresprobe Sciences.^{8,9} Bilirubin binding capacity (BBC) and related measures will be measured with hematofluorometry within 12 hours of sampling.^{10,11} Total FFA will be measured at UT Houston SOM.

Per usual care, lipids start at 1 g/kg/day and advance by 1 g/kg/day to a max of 3 g/kg/day as tolerated by the neonate. Blood samples will be collected when lipids are at the following amounts as listed below:

Blood Sampling Schema:

Lipid Dose (g/kg)	Total sample in (mL)
1	0.5
2	0.5
3	0.5
3	0.5
Total	2.0

Two samples will be obtained with the lipid emulsion at 3 g/kg/day in order to follow these values in a steady state at the maximum dosage.

Safety Precautions:

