Unrelated to comparisons between Intralipid and SMOF, a number of analyses will address important questions. Hematofluorometry is the methodology employed to measure bilirubin binding capacity (BBC). With total serum bilirubin (TSB) and Bf, BBC is one of three measured components in the bilirubin binding panel proposed by Ahlfors.^{10 11 12} Calculated components of the bilirubin binding panel include reserve bilirubin binding capacity (RBBC), calculated as the difference between BBC and bound bilirubin, and the bilirubin-albumin equilibrium dissociation constant (Kd). The clinical problem of unrecognized high Bf levels secondary to FFAs displacing bilirubin from albumin is a prime example of the potential utility of the bilirubin binding panel, and the limitations of relying on TSB alone. The question arises: should clinicians also measure BBC and Bf, and perhaps FFA, as they prescribe lipid emulsion during the first weeks after birth? The value of including BBC and RBBC in the bilirubin binding panel in addition to Bf is that the former measures should be give an earlier and more reliable danger signal. This is because Bf levels remain relatively stable until binding capacity is reached, then rises quadratically – such that the danger signal may only be appreciated too late. However, the capacity of hematofluorometry to detect FFAs effect on BBC in the clinical setting is uncertain. Specifically, there is a step in the measurement method that could, in theory, displace FFA from albumin such that the *in-vivo* effect on RBBC might be underestimated. In the current study, we can test the capacity of hematofluorometry to detect the effect of FFA on BBC in the following manor. To the extent that elevated Bf levels are caused by FFAs displacing bilirubin from albumin binding sites, measured BBC should decrease as Bf levels rise. It is believed that this phenomenon becomes when the molar ratios of FFA to albumin exceed ~4:1 (Amin, Maisels, Watchko, 2017).² However, it is necessary to measure and adjust for concurrent changes in albumin concentrations because this also affects both Bf and BBC.

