The hematofluorometry saturation index, calculated as bound bilirubin divided by RBBC, provides a second means by which the capacity of hematofluorometry to detect displacement of bilirubin from albumin by FFAs can be evaluated. The saturation index (SI) has been reported to have a tight correlation with Bf (figure 2).¹³ However, the correlation is dependent on accurate measurement of BBC and RBBC. Finding that the correlation of SI and Bf persists at high Bf levels despite high FFA levels would provide evidence that BBC and RBBC are measured accurately under these conditions. Conversely, finding that SI-Bf correlation deteriorates as FFA and Bf levels rise would provide evidence that hematofluorometry may not be suitable for guiding decisions regarding phototherapy and lipid infusions for premature newborns. It is acknowledged that these analyses are dependent on observing adequate variation in FFA and Bf levels, and that FFA reach levels that are high enough to displace bilirubin from albumin – all of which have been observed in previous similar studies.¹

[figure not shown]

Fig. 1. A plot of the apparent unbound bilirubin concentration as determined by the “peroxidase” method (U) vs the ratio of albumin-bound bilirubin to reserve bilirubin binding capacity as determined with the hematofluorometer (B/R) for a series of specimens prepared by addition of bilirubin to blood obtained from a single adult donor

Figure 2

References

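### The test of whether hematofluorometry detects FFA displacement relates BBC to Bf rather than to measured FFA, so an assay blind to FFA can pass it

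*Combined protocol and SAP*

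**What the plan says.** The Observational Outcomes section states its aim: "we can test the capacity of hematofluorometry to detect the effect of FFA on BBC". The worry behind it is that "there is a step in the measurement method that could, in theory, displace FFA from albumin", so that the in-vivo effect on reserve capacity (RBBC) would be underestimated.

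The criterion is that, to the extent FFA displacement is the cause of high Bf, "measured BBC should decrease as Bf levels rise". One adjustment is named: "it is necessary to measure and adjust for concurrent changes in albumin concentrations because this also affects both Bf and BBC". The section says displacement is thought to matter when "the molar ratios of FFA to albumin exceed ~4:1", but does not make that ratio a model term, stratum or cut-off.

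The same section defines RBBC: "calculated as the difference between BBC and bound bilirubin". It then introduces the saturation index (bound bilirubin over RBBC), which is reported to track Bf closely and which "provides a second means by which the capacity of hematofluorometry to detect displacement of bilirubin from albumin by FFAs can be evaluated". Persistence of the index-Bf correlation at high FFA counts for the method, and deterioration counts against it.

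Methods plans "2 methods for measuring free fatty acid – both bound and unbound free fatty acids", together with albumin and four samples per infant across lipid doses. Data Analysis names multilevel regression, for dose responses only.

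**The concern.** The question is about FFA, but FFA enters the criterion only as a premise about why Bf is high. The relation to be examined is between BBC and Bf, and Bf is itself a function of BBC. An infant whose albumin binds less bilirubin for some other reason has both a lower BBC and a higher Bf. That produces the predicted inverse slope whether or not the assay sees FFA. The plan recognises one such shared cause, albumin concentration, and adjusts for that one alone.

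The section asks whether clinicians should measure BBC while prescribing lipids, on the argument that BBC and RBBC give an earlier warning than Bf. A false positive would lend support to a monitor that misses the displacement it is meant to detect.

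**Working it through.** **Plan's figure.** None is attached to this analysis. The plan's only design figure, power 0.81 for the primary Bf comparison, reproduces: 31 per group, 15.9 versus 22.1, SD 8.5, two-sided alpha 0.05 gives 0.807 by the t test.

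**Algebra.** The plan's definitions, with a dissociation constant Kd and bound bilirubin B, imply

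Bf = Kd × B / (BBC − B).

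Bf falls as BBC rises at fixed B, and rises with B at fixed BBC. For illustration, assume capacity 380 µmol/L and B = 100 µmol/L:

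- Baseline: 100/280 = 0.357.
- Capacity 10% lower for a non-FFA reason (342): 100/242 = 0.413. Bf rises by 280/242 = 1.16 while BBC falls by 10%. This is the predicted pattern with no FFA involved.
- Bilirubin 30% higher (130), capacity unchanged: 130/250 = 0.520. Bf rises by 0.520/0.357 = 1.46 and BBC does not move. This is noise for the test.

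**Simulation of a blind assay.** All inputs are assumptions, because the documents give no distributions: 64 independent samples; albumin 380 (SD 55) µmol/L; bound bilirubin median 100 µmol/L, log-SD 0.3; FFA:albumin ratio median 3, log-SD 0.5; assay error 10% for Bf and 5% for BBC. Log BBC was regressed on log Bf and log albumin. A positive is a Bf slope with t < −2.0 (nominal rate about 2.5%).

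| Non-FFA spread in BBC at fixed albumin | No FFA effect | Moderate FFA effect | Strong FFA effect |
|---|---|---|---|
| 0% | 2.4% | 2.3% | 2.5% |
| 5% | 13.8% | 11.8% | 7.5% |
| 10% | 60.1% | 44.9% | 33.2% |
| 15% | 92.4% | 82.9% | 64.1% |

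The 0% row is the case where bilirubin varies but non-FFA capacity does not: there is no excess of false positives. A separate simulation with other illustrative inputs gave about 2%, 11%, 49% and 83% at the same four spreads.

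**Can the test tell the two assays apart?** With a moderate FFA effect and an assay that does see FFA, the BBC-Bf test was positive in 95.3%, 99.4% and 99.9% of runs at 0%, 10% and 15% spread. Dividing by the blind-assay rates, a positive result favours a seeing assay by 0.953/0.023 = 41 at zero spread, 0.994/0.449 = 2.2 at 10% and 0.999/0.829 = 1.2 at 15%.

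**Measured FFA as the predictor.** BBC regressed on the FFA:albumin ratio, with albumin and bound bilirubin as covariates, was positive in about 2-3% of runs for the blind assay (about 6% if bilirubin and capacity correlate at −0.5) and about 100% for the seeing assay. Adjusted for albumin alone, in the separate simulation, the figures were 2-3% and 79-100%.

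**Adding terms to the BBC-Bf model.** At 10% spread and a moderate FFA effect, adding bilirubin raised the blind-assay rate from 0.45 to 0.84. Adding bilirubin and FFA together, in the separate simulation, raised it from 0.49 to 1.00. With both held fixed, non-FFA capacity is the main source of variation left in Bf, so the slope picks it up more clearly.

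**Within infants.** With repeated samples, a within-infant BBC-Bf slope was falsely positive in about 2-4% of runs if non-FFA capacity is stable within an infant. With 5% within-infant drift the rate was 45-50% in one set of assumptions and over 70% in another.

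**The case against.** The strongest defence has four parts.

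- **The plan does use FFA elsewhere.** The saturation-index check brings FFA in and can expose a blind assay. With a moderate effect, the simulated index-Bf correlation was 0.82 above a 4:1 ratio against 0.96 below it; with a strong effect, 0.41 against 0.90. A reader might infer that the plan has no safeguard at all, and that would be wrong. But the plan presents that check as a second means, gives no model or definition of deterioration, and has no rule for the case where the two tests disagree. The BBC-Bf test therefore still counts as evidence on its own.
- **The criterion is an expectation, not a decision rule.** No slope, p-value or model is stated, and the reference to concurrent changes in albumin permits a within-infant reading. That stands, and such a reading would remove most of the problem if non-FFA capacity is stable within infants. It does not supply the missing FFA term, and the false positives return if capacity drifts.
- **High bilirubin is not a cause of false positives.** A reader might infer that variation in total bilirubin also makes a blind assay look good. The 0% row shows that it does not. It adds noise and can hide a real effect. It matters for false positives only through correlation with capacity: at 15% spread the rate was 100% with correlation −0.5 and 2% with +0.5.
- **The outcome is observational.** It is separate from the Intralipid-SMOF comparison, and the data for the direct analysis are to be collected anyway. That limits the stakes, and also makes the correction cheap.

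**Conclusion.** The concern holds for the BBC-Bf criterion. A fall in measured BBC as Bf rises, adjusted only for albumin, does not show that the assay detects FFA, because non-FFA variation in BBC gives the same slope.

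The false-positive direction is conditional on such variation existing, between infants or, in a within-infant model, within them. The documents do not say how large it is. The illustrative cross-sectional rates run from the nominal 2-3% at zero spread to about 50% at 10% and over 80% at 15%. They rest on assumed inputs and should not be read as estimates for this trial. It would also go too far to say that the plan will reach a wrong conclusion: the saturation-index check may contradict a false positive, and the analysts may choose a within-infant model. The primary comparison of Bf between emulsions is not touched.

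**What to change.** Rewrite the criterion as a multilevel regression of measured BBC on measured FFA, adjusted for albumin, with a patient random effect or a term for within-infant change across doses. Use the FFA:albumin molar ratio where total FFA is measured, and unbound FFA at every sample. The secondary outcomes appear to list total FFA only for the second day at 3 g/kg/day; if it is measured only then, the within-infant part rests on unbound FFA. The simulated rates above are for the ratio model; the unbound-FFA version was not simulated.

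State that the method will be said to detect displacement only if BBC falls as FFA rises. Report any BBC-Bf relation as descriptive, and do not rely on adding total bilirubin or FFA to it as a repair.

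The cost is the wording of one exploratory analysis. FFA, albumin and BBC are already planned measurements, so no further infants, samples or assays are needed.

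### Exploratory hematofluorometry analysis: a persisting SI-Bf correlation is weak evidence that BBC and RBBC are accurate; add Bf/SI (in effect Kd) against FFA

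*Combined protocol and SAP*

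**What the plan says.** All references are to the combined protocol and SAP. Observational Outcomes sets this work apart from the Intralipid-SMOF comparison and asks whether hematofluorometry can detect FFA displacing bilirubin from albumin. The stated worry is that a step in the assay may itself remove FFA from albumin, so that the in-vivo "effect on RBBC might be underestimated".

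Two checks follow.

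- **BBC against Bf.** If displacement drives Bf up, "measured BBC should decrease as Bf levels rise". The section adds that "it is necessary to measure and adjust for concurrent changes in albumin concentrations".
- **SI against Bf.** SI is defined as bound bilirubin over RBBC. The rule for a favourable result reads: "correlation of SI and Bf persists at high Bf levels despite high FFA levels would provide evidence that BBC and RBBC are measured accurately". The rule for an unfavourable one reads: "finding that SI-Bf correlation deteriorates as FFA and Bf levels rise would provide evidence that hematofluorometry may not be suitable". The use in view is to guide phototherapy and lipid decisions.

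The support offered for the second check is that "The saturation index (SI) has been reported to have a tight correlation with Bf". The caption of the figure cited for this says the plot is "for a series of specimens prepared by addition of bilirubin to blood obtained from a single adult donor".

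Kd is listed among the calculated components of the binding panel, but no analysis of it is described. Data Analysis mentions multilevel regression only for dose responses. No section states a slope, a Bf/SI comparison or a Kd comparison against FFA, or what size of correlation counts as persisting.

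**The concern.** A correlation describes how tightly points follow a line, not how steep the line is. If the instrument misses displacement, RBBC is overstated and SI is too low for the Bf actually present, so Bf per unit SI goes up. Where that shift is similar across the samples being correlated, the points move to a steeper line and stay just as close to it.

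The cited tight correlation does not settle the matter. Adding bilirubin to one donor's blood varies bilirubin. It does not show what happens to the relation when FFA varies.

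What is at stake is the conclusion of this section alone. It is meant to inform whether the instrument suits phototherapy and lipid decisions, and under some conditions its rule would count the feared error as evidence of accuracy.

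**Working it through.** The plan states no correlation, slope, cut-off or sample count for this analysis, so there is no figure of its own to reproduce. The only nearby figure, power 0.81 for the primary Bf comparison, does reproduce (0.807 by the t distribution, 31 per arm, difference 22.1 − 15.9 = 6.2 nM, SD 8.5, two-sided 0.05). It is not touched by this point.

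**1. What the feared error does.** Let B be bound bilirubin and R be RBBC = BBC − B. The plan defines SI = B/R. Mass action, which the documents do not write out, gives Bf = Kd × B/R(true). Hence

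Bf / SI(measured) = Kd × R(measured) / R(true).

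With accurate R the ratio is Kd. If a fraction f of capacity is lost to FFA and the instrument misses it, R(measured) = BBC − B while R(true) = BBC(1 − f) − B.

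Assumed values: BBC 20 (SD 2) and B 6 (SD 1.5) in arbitrary units, baseline Bf/SI 30 nM, Bf log-noise SD 0.15, 64 samples, f common to all. At the means R(measured) = 20 − 6 = 14.

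| Missed loss f | R(true) = 20(1 − f) − 6 | 14 / R(true) | Simulated median Bf/SI | Simulated Pearson r |
|---|---|---|---|---|
| 0% | 14 | 1.00 | 30 | 0.93 |
| 10% | 12 | 1.17 | 35 | 0.93 |
| 20% | 10 | 1.40 | 42 | 0.94 |
| 30% | 8 | 1.75 | 53 | 0.94 |
| 40% | 6 | 2.33 | 71 | 0.91 |

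The ratio more than doubles while r barely moves.

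**2. How far this depends on the setting.** A fuller simulation (400 to 500 runs per setting) compared an accurate instrument with one blind to FFA. All of the following inputs are assumptions:
- 64 infants with up to 4 samples each (64 × 4 = 256)
- bound bilirubin median 35% of mean capacity, log-SD 0.4, capped at 90% of worst-case capacity
- albumin log-SD 0.10
- FFA:albumin uniform from 1 to 8
- Bf error 10%; BBC error 5% or 10%
- loss starting at the section's ~4:1 ratio, either constant above it or rising linearly to its full size at 8:1.

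Correlations are on the log scale. A blind instrument counts as flagged when its r falls below the accurate instrument's 5th percentile. That is an idealised cut-off which the plan does not have. Results are for losses of 20/30/40%.

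*High-FFA samples only* (FFA:albumin above 4, top-quartile Bf):
- Constant loss, 5% BBC error: blind r 0.94/0.93/0.91, accurate 0.94/0.91/0.88. With 10% error: 0.85/0.81/0.79 against 0.84/0.79/0.75. Flagged in 0 to 7% across repeated simulations.
- Graded loss, 5% error: blind r 0.87/0.69/0.43, accurate 0.92 to 0.94. Flagged in 84/100/100% with 256 samples and 40/73/99% with 64. With 10% error: 26/83/100% and 15/37/70%.

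*All samples pooled:*
- Constant loss, 5% error: r falls from 0.98 to 0.93/0.87/0.77. Flagged in 80 to 100% over both error levels and both sample counts.
- Graded loss: flagged in 86 to 100% with 256 samples and 40 to 100% with 64.
- On the untransformed scale sensitivity is often low, down to 13% with 64 samples and constant loss.

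**3. The direct measure.** Median Bf/SI at high against low FFA is 1.2 to 1.5 times (graded) or 1.5 to 2.7 times (constant) with the blind instrument, and 1.00 with the accurate one. Regressing log(Bf/SI) on FFA with 64 values flags the blind instrument in 98 to 100% of runs and the accurate one in 1 to 5%, against a nominal 2.5%.

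**The case against.** The strongest reply is that the section never confines the correlation to a high-FFA subset. It gives no quartile or FFA cut for this check, it speaks of the correlation deteriorating as FFA and Bf rise, and it says the analyses need adequate variation in both. That wording fits a comparison across the range at least as well, and pooled r does drop. A step to full loss at 4:1 with nothing further up to 8:1 is likewise an assumption, because the section says only that displacement matters once the ratio exceeds about 4:1. Both points stand. A reader might infer that correlation simply cannot see the error, or that the rule would generally pass a faulty instrument. The documents do not support that. It follows only for samples sharing a roughly common shift.

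The reply does not rescue the rule. With no cut-off or comparator, a pooled r of 0.87 to 0.93 could easily be reported as a correlation that persists. A fall in r is also non-specific: noise and restricted range lower it too.

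The section is also hedged. It speaks of evidence rather than proof, and it presents SI as a second route beside the albumin-adjusted BBC check. That is fair, but the BBC check relates BBC to Bf and is not a test of Bf/SI against FFA.

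Finally, Bf/SI has weaknesses of its own. With an accurate instrument, a true Kd rise of 20% or 50% at 8:1 makes the slope significant in 81 to 84% or 100% of runs. Between-infant Kd variation (SD 10 to 20%) correlated +0.3 with FFA does so in 26 to 50% with 64 values. Bf/SI should therefore not stand alone as the deciding test.

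**Conclusion.** The point holds in conditional form, as a cheap improvement to an exploratory analysis. Persistence of the SI-Bf correlation should not by itself be taken as evidence that BBC and RBBC are accurate. Within high-FFA samples with a roughly constant missed loss, r is essentially unchanged and the rule would read the error as accuracy. With graded loss or pooling across FFA, r carries real but indirect information that the plan has no stated way to judge.

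The mechanism rests on mass action and the plan's own definition of SI. The sizes rest on assumed distributions and loss shapes and are illustrative. Nothing here shows that hematofluorometry is inaccurate, and the randomized comparison is unaffected.

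**What to change.** - Keep the SI-Bf correlation as a descriptive result, and remove its persistence as a stand-alone criterion of accuracy.
- Add a regression of log(Bf/SI), in effect log Kd, on FFA. Use the FFA:albumin molar ratio where total FFA is measured and FFAu otherwise. Report the slope with its 95% CI.
- Beside it, report measured BBC on the same FFA measure with albumin as covariate, and interpret the two together. BBC falling with FFA while Bf/SI stays flat is consistent with displacement being detected. BBC flat while Bf/SI rises is consistent with displacement being missed.
- Where FFAu is repeated, use an infant random intercept, split FFAu into the infant mean and the deviation from it, and read the within-infant slope. In the between-infant Kd scenario above, with SD 20%, the within-infant slope flagged an accurate instrument in 3% of runs, against 34 to 39% with a random intercept alone (128 values).
- State two limits: a rise in Bf/SI with FFA cannot by itself separate missed displacement from a true FFA effect on Kd, and between-infant Kd differences related to FFA can raise the cross-sectional slope of an accurate instrument.

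The cost is slightly more analysis work, with no new blood or assay. The main constraint is data. Secondary outcomes lists total FFA only for the second day at 3 g/kg/day (at most 64 values, one per infant) and FFAu for both days (at most 64 × 2 = 128), so within-infant slopes must rely on FFAu. Variation between two days at one dose may be small. The sponsor should confirm whether FFAu is also measured on the 1 and 2 g/kg/day samples in the Blood Sampling Schema, which would widen the within-infant contrast.

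### A weaker SI–Bf correlation at high Bf may reflect range restriction and magnified BBC error, so it is a poor sign that hematofluorometry misses FFA displacement

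*Combined protocol and SAP*

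**What the plan says.** Observational Outcomes proposes two ways to test whether hematofluorometry detects displacement of bilirubin by FFA. The second uses the saturation index, "calculated as bound bilirubin divided by RBBC", where RBBC is "calculated as the difference between BBC and bound bilirubin". The reading rule has two sides:

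- Favourable: "Finding that the correlation of SI and Bf persists at high Bf levels despite high FFA levels would provide evidence that BBC and RBBC" can be trusted.
- Unfavourable: "finding that SI-Bf correlation deteriorates as FFA and Bf levels rise would provide evidence that hematofluorometry may not be suitable" as a guide to phototherapy and lipid infusion.

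The section accepts that "the correlation is dependent on accurate measurement of BBC and RBBC" and that "these analyses are dependent on observing adequate variation in FFA and Bf levels". The tight correlation it uses as background is Figure 2, which shows specimens made by adding bilirubin to one adult donor's blood.

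Neither this section nor Data Analysis gives a subgroup, cut-off, type of correlation, threshold, test or handling of repeated samples for this analysis. The multilevel regression in Data Analysis is for dose responses. Albumin adjustment is mentioned for the BBC analysis, not for SI and Bf.

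**The concern.** This point is about the unfavourable side of the rule. Two features of the analysis can lower r at high Bf even when hematofluorometry reads BBC without any FFA-related error.

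1. Bf is one of the two correlated variables. Looking only at high-Bf samples cuts its range, and r falls with range.
2. RBBC is a difference that shrinks as saturation rises. The same percentage error in BBC becomes a larger percentage error in RBBC, and so in SI, where Bf is highest.

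A drop in r therefore does not separate missed FFA displacement from ordinary measurement behaviour. At stake is an unsupported conclusion about a method that the protocol discusses as a possible guide to care.

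**Working it through.** **The plan's own figure.** The plan gives none for this analysis. Its only power figure is 0.81 for the Bf comparison with 31 per arm, a difference of 6.2 nM and SD 8.5. A two-sided t test reproduces it (0.807), but it has no bearing here.

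**Error growth in SI.** Write B for bound bilirubin, C for BBC and s = B/C for saturation. From the plan's definitions, SI = B/(C − B). To first order, the relative error in SI equals the relative error in C × C/(C − B), which is the relative error in C × 1/(1 − s).

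| Saturation | Factor 1/(1 − s) | A 5% BBC error becomes |
|---|---|---|
| 20% | 1.25 | 6.25% |
| 50% | 2.0 | 10% |
| 80% | 5.0 | 25% |

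No FFA term enters.

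**Range restriction.** For a bivariate normal with constant error, let v be the variance of Bf in the subset divided by its overall variance. Then r′ = r√v / √(r²v + 1 − r²).

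- Either half: v = 1 − 2/π = 0.363.
- Either outer third: v = 1 + 0.431 × 1.091 − 1.091² = 0.280.
- Overall r = 0.90, half: 0.90 × 0.603 / √(0.81 × 0.363 + 0.19) = 0.78.
- Overall r = 0.90, outer third: 0.90 × 0.529 / √(0.81 × 0.280 + 0.19) = 0.74.
- By the same formula, 0.95 becomes 0.85 in an outer third, and 0.80 becomes 0.63 in a half and 0.58 in an outer third.

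**Both together, with no FFA fault.** Each simulated trial had 64 infants, one sample each, a split at median Bf, and Bf = Kd × SI. Bf was 15.9 ± 8.5 nM, the Intralipid figure in Power and Sample Size. The other inputs are assumptions, because the documents give none: mean SI 0.2, 0.5 or 1.0; BBC error CV 5% or 10%; Bf assay CV 5%; bound bilirubin CV 3%; between-infant Kd spread 0 or 20%; Bf lognormal or truncated normal. There were 1,500 trials per setting. Four of the settings:

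| Bf shape | Mean SI | BBC CV | Kd spread | r low half | r high half | r all | High below all | High below low |
|---|---|---|---|---|---|---|---|---|
| Lognormal | 0.2 | 5% | 20% | 0.76 | 0.82 | 0.90 | 99% | 30% |
| Lognormal | 1.0 | 10% | 0 | 0.79 | 0.70 | 0.82 | 94% | 72% |
| Truncated normal | 0.2 | 5% | 20% | 0.84 | 0.69 | 0.88 | 99.7% | 91% |
| Truncated normal | 1.0 | 10% | 0 | 0.85 | 0.56 | 0.80 | 99% | 98% |

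Over all settings, high-half r was below overall r in 92–100% of trials. It was below low-half r in 30–72% with lognormal Bf and 91–99.5% with truncated normal Bf.

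**Does the drop in r detect a real fault?** The fault was BBC overstated by up to 20% as FFA rises. Two tests were compared: a one-sided Fisher test of high-half against low-half r, and the FFA coefficient in a regression of log SI on log Bf and FFA over the full range.

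| Test | Flags with no fault | Flags with fault |
|---|---|---|
| Fisher, lognormal Bf | 2–23% | 2–23% |
| Fisher, truncated normal Bf | 44–83% | 45–87% |
| FFA coefficient | 4–7% | 32–99.9% |

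Comparing correlations hardly distinguishes the two states. The FFA coefficient does.

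**The case against.** A reader might infer that the plan will split the data by Bf and that an unbiased instrument is bound to show a falling correlation. The documents do not support that. They name no split, and the wording joins FFA with Bf, so a scatter plot or a regression on FFA would also satisfy it. Range restriction acts equally on both outer thirds (0.90 becomes 0.74 in each), so alone it produces no decline from low to high Bf. With right-skewed Bf the high half has the wider range and can show the higher r (0.82 against 0.76 above). In a further no-fault simulation (saturation 0.45 ± 0.15, BBC error 3%, Bf error 10%), r in the bottom, middle and top thirds was 0.94, 0.78 and 0.93, which is essentially no fall from bottom to top. All of this stands, and it limits the claim to one of possible misfire.

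It can also be said that magnified error at high saturation is real imprecision in SI and so bears on suitability. That stands too. But it is not evidence that FFA displacement is missed, which is what this analysis is meant to test.

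Finally, the plan already asks for adequate variation in FFA and Bf. That caveat concerns the data as a whole. It does not address range within a high-Bf subset or error growth as RBBC shrinks. The analysis is observational and separate from the comparison of emulsions, so the consequence is modest.

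**Conclusion.** The point holds as a weakness in a stated criterion. A lower SI–Bf correlation at high Bf may appear with no FFA-related fault. Under the assumed assay errors it is close to certain (92–100% of simulated trials) if the reference is the overall correlation. Figure 2 is an unsafe reference as well, because one donor's blood carries no between-infant variation. A fall from low to high Bf is much less certain, about 30% to over 90%, depending on the Bf distribution, saturation and assay errors. The error factor is algebra from the plan's definitions. The simulated frequencies rest on assumed inputs and one sample per infant. No treatment comparison or sample size is affected, so this is a low-priority improvement.

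**What to change.** State in Observational Outcomes that correlations at different Bf levels will not be compared. Over the full Bf and SI range, model the log Bf–log SI relation with the measured FFA:albumin ratio and albumin as covariates and a random infant effect. Take the systematic shift with FFA:albumin (its coefficient with 95% CI) as the main evidence that hematofluorometry misses FFA displacement. Report residual scatter by FFA:albumin as secondary.

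The shift comes first because the fault the protocol fears is a bias, an underestimated effect on RBBC. With BBC overstated by 20% in a high-FFA group, simulated mean log Bf at the same SI moved by 0.31–0.33 (e^0.31 = 1.36 and e^0.33 = 1.39, so 36–39%). In one setting residual SD only went from 0.114 to 0.130. In a separate simulation of overstatement by up to 20%, comparing residual SDs flagged about 6% of trials, no better than chance.

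The direction of the regression should be specified. With log Bf as response, error in SI flattens its slope. Because FFA and Bf tend to rise together, the FFA coefficient can then pick up a false shift of the same sign as a real fault. The 4–7% false-flag rate above was obtained with log SI as response, so that version should at least be a sensitivity analysis. Since Bf = Kd × SI, a true change of Kd with FFA would also appear as a shift, and the text should say so.

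The cost is a paragraph of analysis text and a slightly longer exploratory analysis. Methods already lists albumin, BBC and both FFA measures. The total FFA outcome names only the second day at 3 g/kg/day, so the plan should confirm which samples will have the ratio.
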